7.2.1.5 Frequent ($\geq 5\%$) Adverse Events by System Organ Class and Preferred Term

TEAEs occurring for more than 5% of the subjects in any of the two treatment groups in Part 1 or any of the four treatment groups in Part 2 will be summarized by SOC and PT in decreasing frequency separately.

7.2.1.6 Adverse Events of Special Interest

The Adverse Events of Special Interest (AESI) categories by SOC and PT will be summarized and presented by the two treatment groups in Part 1 and by the four treatment groups in Part 2. The details of AESI list and search criteria are stated in Appendix A, which are extracted from Adalimumab Product Safety Statistical Analysis Plan Version 8.0.

7.2.2 SAEs (Including Deaths) and Adverse Events Leading to Study Drug Discontinuation

All serious adverse events (SAEs), deaths, and adverse events leading to discontinuation of study drug will be listed. The number and percentage of subjects experiencing SAEs (including deaths) and adverse events leading to discontinuation of study drug will be tabulated according to the primary MedDRA SOC and MedDRA PT for each treatment group in Part 1 and for each treatment groups in Part 2.

7.3 Analysis of Laboratory Data

7.3.1 Analysis for Continuous Laboratory Data

Observed values of hematology, chemistry, and urinalysis variables which are measured longitudinally will be summarized by visits and by the two treatment groups in Part 1 and by the four treatment groups in Part 2. The following summary statistics of each visit will be presented for each treatment group: sample size, observed mean, standard deviation, minimum, median, and maximum.

Mean change and percent change from baseline in selected laboratory variables will be summarized by the two treatment groups in Part 1 and by the four treatment groups in Part 2 at each visit. Mean difference between the two treatment groups in Part 1 will be compared using one-way ANOVA with treatment as a factor. Mean difference and the associated 95% CIs will be presented at each visit. The selected laboratory variables of clinical interest include: Hematocrit, hemoglobin, Red Blood Cell (RBC) count, White Blood Cell (WBC) count, platelet count, lymphocytes, neutrophils, creatinine, Aspartate aminotransferase (AST), aminotransferase (ALT), Cholesterol, Glucose, Triglycerides.

The last evaluation prior to the first dose of study drug in Part 1 or Part 2 will be used as Baseline for Part 1 or Part 2, respectively.

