8.1.5 Statistical Analyses of Safety

Safety analyses will be carried out using safety population, which includes all subjects that received at least one dose of study medication. Treatment-emergent AEs will be summarized and reported.

Treatment-emergent AEs are defined as AEs that begin either on or after the first dose of the study medication, and up to within 70 days after the last dose of the study medication. All treatment emergent AEs will be coded using the Medical Dictionary for Drug Regulatory Activities (MedDRA[®]). The number and percent of subjects experiencing AEs will be tabulated by system organ class and preferred term. In addition, a summary of AEs by severity and relationship to study drug will be presented. AEs, which are serious, severe, or life-threatening, which lead to premature study discontinuation will be listed and described in detail. Adverse event of special interest (AESI) will also be tabulated.

Observed values of vital signs and laboratory variables at each visit will be summarized for all treated subjects, and change from baseline in selected lab variables will be compared between treatment groups using a one way ANOVA. The last evaluation prior

to the first dose of study drug will be used as Baseline for the analyses in Part 1. For selected parameters, a listing of all subjects with any laboratory determination meeting Common Toxicity Criteria (CTC) (Version 3) of Grade 3 or higher will be provided. Shift tables for changes from Baseline according to the normal range will also be provided for laboratory variable.

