4.7 Missing Data Imputation

The following missing data imputation will be performed for efficacy analysis.

Non-Responder Imputation (NRI) Approach

To account for missing data for the binary efficacy endpoints, a non-responder imputation approach (NRI) will be used, e.g., subjects who have missing data at a specific visit will be treated as non-responder for that visit, or who prematurely discontinue or have been rescued will be considered as a non-responder for all subsequent visits.

Mixed-Effects Model Repeated Measures (MMRM)

The repeated measure analysis will be conducted using mixed models based on observed data at all visits. For the MMRM analysis (of continuous variables), data collected after premature discontinuation of study drug will be excluded. The mixed model includes treatment, visit, treatment-by-visit interaction, and the stratification factor of duration of prior MTX use (≤ 3 months or > 3 months) as fixed effects, subject as random effect and baseline measurement as a covariate. An unstructured variance covariance matrix will be used. The parameter estimations assume data being missing at random (MAR) and using the method of restrictive maximum likelihood (REML).

Observed Cases (OC)

The OC analysis will not impute values for missing evaluations, and thus a subject who does not have an evaluation on a scheduled visit will be excluded from the OC analysis for that visit. In addition, OC will not include values after subject have rescue visit or after premature discontinuation of study drug.

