5.0 Analysis Populations and Important Subgroups

5.1 Analysis Populations

Intent-to-Treat Population Part 1

The Intent-To-Treat Part 1 (ITT Part 1) population comprises all subjects who were randomized and received at least one dose of the study medication during the Part 1 period. The data collected up to Week 16 will be included and analyzed by the treatment

group assignment given at the time of randomization, even if the subject does not receive the correct treatment, is not compliant to the protocol procedures, or does not follow the protocol until completion.

Intent-to-Treat Population Long Term

The Intent-To-Treat Long Term (ITT LT) population comprises all subjects who entered Part 2 period and received at least one dose of Part 2 study medication. The data collected from randomization and up to Week 32 will be included and analyzed by the four treatment regimens as follows:

- ADA 40 mg eow + MTX 15 mg ew/ADA 40 mg eow
- ADA 40 mg eow + MTX 15 mg ew/ADA 40 mg ew + MTX 15 mg ew
- MTX 20 - 25 mg or highest tolerable dose ew
- MTX 20 - 25 mg or highest tolerable dose ew/ADA 40 mg eow + MTX 20 - 25 mg or highest tolerable dose ew

Per Protocol Population

In order to evaluate the impact of major protocol violations on the results of the trial, additional analysis of the primary effectiveness variable may be conducted on the per protocol population, which consists of all ITT Part 1 subjects who entered the randomized period of the study and did not meet any major protocol violation during the Part 1 of the study. The determination of major protocol violation will be finalized prior to the final database lock.

Safety Population Part 1

The Safety population Part 1 consists of all subjects who received at least one dose of the study medication during the Part 1 period. The data collected up to Week 16 will be included and analyzed by the two "As treated" treatment groups in Part 1. "As treated" is determined by the treatment a subject received during majority of the subject's drug exposure time in the analysis period, regardless of the treatment randomized.

Safety Population Part 2

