7.0 Safety Analyses

7.1 General Considerations

There will be 2 sets of safety analyses to be performed.

1. Safety analyses during Part 1 (up to Week 16).
2. Safety analyses during Part 2 (Week 16 to Week 32).

Safety analyses will include reporting of adverse events (AEs), laboratory, and vital signs measurements. Treatment-emergent AEs will be summarized and reported. Missing safety data will not be imputed. Part 1 and Part 2 safety analyses will be carried out using the Safety Population Part 1 and Safety Population Part 2, respectively.

Safety Analysis during Part 1 (up to Week 16)

Standard safety analysis by the "as treated" treatment groups of ADA 40 mg eow + MTX 15 mg ew and MTX 20 - 25 mg or highest tolerable dose ew will be performed on safety data up to Week 16. No protocol-defined treatment switching will occur prior to this time point.

Frequency tables of subjects with treatment-emergent adverse events (TEAEs) by system organ class (SOC) and by preferred term (PT) as in the Medical Dictionary for Regulatory Activities (MedDRA) dictionary will be provided by as-treated treatment groups.

Observed values in all continuous laboratory parameters and vital signs variables at each visit will be summarized by "as treated" treatment groups. Frequency tables of subjects meeting criteria for potentially clinically significant vital sign values and for potentially clinically significant laboratory values will be provided by as-treated treatment groups. Missing safety data will not be imputed.

Safety Analysis during Part 2 (Week 16 to Week 32)

Similar standard safety analysis by the "as treated" treatment groups will be performed on safety data from Week 16 to Week 32 based on Safety Population Part 2.

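### Part 1 laboratory changes are compared by one-way ANOVA without the baseline value as a covariate: valid, but less precise than it could be for most variables

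*SAP*

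**What the plan says.** SAP 7.3.1 describes the laboratory outcome as follows: "Mean change and percent change from baseline in selected laboratory variables will be summarized". For Part 1 it then gives the between-arm method: "Mean difference between the two treatment groups in Part 1 will be compared using one-way ANOVA with treatment as a factor". The output is an interval per visit: "Mean difference and the associated 95% CIs will be presented at each visit". Thirteen variables are listed: hematocrit, hemoglobin, red and white cell counts, and "platelet count, lymphocytes, neutrophils, creatinine, Aspartate aminotransferase (AST), aminotransferase (ALT), Cholesterol, Glucose, Triglycerides". The section also defines baseline, as the last evaluation before the first dose of the Part concerned.

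Protocol 8.1.5 agrees: "change from baseline in selected lab variables will be compared between treatment groups using a one way ANOVA". The statistical methods part of the synopsis says the same.

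The Part 1 continuous efficacy endpoints are handled differently. Their mixed model in SAP 4.7 and 6.3 has "subject as random effect and baseline measurement as a covariate", together with the randomisation stratum.

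Two features of the safety analysis matter here. The groups are formed by treatment actually received for most of the exposure time, "regardless of the treatment randomized" (SAP 5.1). For gaps in the data, SAP 7.1 says: "Missing safety data will not be imputed".

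**The concern.** Subtracting baseline is not the same as adjusting for it. A change score fixes the slope of the follow-up value on baseline at 1. ANCOVA estimates that slope. When the true within-arm slope is not 1, the change score leaves explainable variance in the error term, and a baseline difference between the groups leaks into the estimated treatment difference.

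The arms differ in MTX dose and in adalimumab exposure, so mean differences in transaminases and cell counts are a fair safety question. This ANOVA is the only planned between-arm laboratory estimate that comes with an interval: SAP 7.3.2 runs no tests on the shift tables, and SAP 7.3.3 gives counts, percentages and listings. Because the groups are as treated and missing values are left missing, balance at a given visit does not rest on randomisation alone.

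**Working it through.** **Inputs.** Method, outcome and variables come from SAP 7.3.1 and protocol 8.1.5. The plan states no target precision for laboratory comparisons, so there is no figure of that kind to reproduce. The only figure borrowed is the sample size in SAP 4.4: 120 per arm with 10% dropout, so 120 × 0.9 = 108 per arm. That sample size reproduces: 40% against 20% at two-sided 0.05 and 90% power needs 109 per arm, and 109 × 1.1 ≈ 120.

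**Assumptions.** The documents give no r and no laboratory SDs. Both are varied below.

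**Formulas.** Let s0 and s1 be the baseline and post-baseline SDs within arm.

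- ANOVA on change: variance proportional to s0² + s1² − 2·r·s0·s1.
- ANCOVA: variance proportional to s1²·(1 − r²).
- The first minus the second is (s0 − r·s1)². This is never negative, and it is zero only when the slope r·s1/s0 equals 1.
- With s0 = s1 the variance ratio is (1 + r)/2, and the interval-width ratio is its square root.
- The half-width at 108 per arm is 1.96 × √(variance × 2/108).

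**Worked case, r = 0.5, equal SDs of 1.** Change-score variance is 1 + 1 − 1 = 1, so the half-width is 1.96 × √(2/108) = 0.267 SD. ANCOVA variance is 0.75, so the half-width is 1.96 × √(1.5/108) = 0.231 SD. The narrowing is 1 − √0.75 = 13.4%.

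**Range.**

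| r | ANOVA half-width (equal SDs) | ANCOVA half-width (equal SDs) | Narrowing, equal SDs | Narrowing, s1/s0 = 1.25 |
|---|---|---|---|---|
| 0.3 | 0.316 | 0.254 | 19.4% | 11.4% |
| 0.5 | 0.267 | 0.231 | 13.4% | 5.5% |
| 0.7 | 0.207 | 0.190 | 7.8% | 1.0% |
| 0.8 | 0.169 | 0.160 | 5.1% | 0.0% |
| 0.9 | 0.119 | 0.116 | 2.5% | 2.5% |
| 0.95 | 0.084 | 0.083 | 1.3% | 9.9% |

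In the last column the gain vanishes at r = 0.8, where the slope is 0.8 × 1.25 = 1. It returns at higher r because the slope then exceeds 1.

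**Simulation.** With 1,500 simulated trials per value of r, equal SDs and 108 per arm, the mean width ratios were 0.809, 0.867, 0.923 and 0.977 for r = 0.3, 0.5, 0.7 and 0.9. The formula gives 0.806, 0.866, 0.922 and 0.975.

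**Baseline imbalance.** If the groups differ at baseline by d, the change-score difference is shifted by (slope − 1) × d. At slope 0.5 that is −0.5·d: half of any baseline difference passes into the estimate with reversed sign. ANCOVA removes this shift when the linear model holds.

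**The case against.** Several points against this stand.

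- **Size.** A reader might infer that all 13 intervals are needlessly wide, or read a 10 to 35% variance saving (r from 0.8 down to 0.3, equal SDs) as narrowing of the interval. The documents support neither. They give no r or SD, the same range corresponds to about 5 to 19% of width, and the gain is nil for a variable whose slope is 1.
- **Role.** A reader might also infer that liver, blood count or lipid safety signals would be missed. They do not depend on these intervals. The plan has shift tables (SAP 7.3.2), Grade 3 or higher counts and listings and a liver listing by multiples of ULN (SAP 7.3.3), and hepatic and hematologic events of special interest (SAP Appendix A). No decision rule uses the ANOVA.
- **Validity.** Baseline is not ignored, because it enters by subtraction. Under randomisation the change-score difference is unbiased. As-treated grouping departs from randomisation only for subjects who mostly received the other arm's treatment, and nothing suggests that this will be common.
- **Consistency.** The contrast with efficacy holds for Part 1 only. Week 32 continuous endpoints are unadjusted summaries (SAP 6.4).
- **Cost.** ANCOVA adds a linearity assumption and is sensitive to extreme baseline values, and protocol 5.2.1 admits ALT and AST up to 3 times ULN. The equal-SD formula does not carry over to percent change.

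These points limit the size and importance of the matter, not its direction. In large samples the baseline-adjusted interval is never the wider one, and neither document gives a reason for leaving baseline out.

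**Conclusion.** The point holds as a minor improvement in precision. The planned ANOVA on change is valid but less efficient than it could be for every listed variable whose within-arm slope on baseline is not 1, and it passes on part of any baseline imbalance between the as-treated groups. With equal SDs the loss is roughly 5 to 13% of interval width for r between 0.8 and 0.5. It is larger at lower r and small at r of 0.9 or above. With post-baseline spread 1.25 times baseline, the loss at r of 0.8 or below is smaller, reaching nil at r = 0.8. The direction is firm; the size rests wholly on assumed r and SDs. Type I error, the primary endpoint and the sample size are not touched.

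**What to change.** In SAP 7.3.1, replace one-way ANOVA on change by ANCOVA on change, with treatment as factor and the baseline laboratory value as covariate, at each Part 1 visit for the selected variables. State that the between-arm comparison applies to change, with percent change summarised descriptively. Add a brief check of linearity and of the influence of high baseline values, chiefly for ALT and AST. Align protocol 8.1.5 and the synopsis so that the documents keep naming one method. Leave the shift tables, Grade 3 or higher outputs and liver listing as they are.

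No new data are needed, because change from baseline already requires the baseline value. The cost is one degree of freedom out of about 216 (2 × 108) subjects, the linearity assumption, one extra model term and the wording change, including the protocol text.

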7.3.2 Shift Table Analyses

Shift tables for changes from Baseline according to the normal range will also be provided for laboratory variable. The baseline and post-baseline laboratory observations will be categorized by grades according to NCI CTC criteria.

For each laboratory variable, shift tables will be generated that cross tabulate the subjects as deemed appropriate by the two treatment groups in Part 1 and by the four treatment groups in Part 2, respectively:

- Category of the baseline value versus category of the final value.
- Category of the baseline value versus maximum category.
- Category of the baseline value versus minimum category.

Note that the minimum/maximum category is used, rather than the category of the minimum/maximum value. The two may be different due to variation in the reference range.

No statistical tests will be performed for this analysis.

7.3.3 Analysis for Potentially Clinically Significant Laboratory Values

For selected laboratory parameters, the criteria for potentially clinically significant laboratory values will be determined by CTC criteria of Grade 3 or above. The number and percentage of subjects meeting the criteria for potentially clinically significant laboratory values will be summarized by the two treatment groups in Part 1 and by the four treatment groups in Part 2.

A listing of all subjects with any laboratory determination during each Part meeting Common Toxicity Criteria (CTC) (Version 3) of Grade 3 or higher will be provided. For each of these subjects, the whole course of the respective parameter will be listed.

A listing of potentially clinically significant liver function laboratory values will be provided. The listing will include all subjects who met any of the following criteria:

- $ALT \geq 3 \times ULN$
- $ALT \geq 5 \times ULN$
- $ALT \geq 10 \times ULN$
- $ALT \geq 20 \times ULN$
- $AST \geq 3 \times ULN$
- $AST \geq 5 \times ULN$
- $AST \geq 10 \times ULN$
- $AST \geq 20 \times ULN$
- $TBL \geq 2 \times ULN$
- $ALP \geq 1.5 \times ULN$
- ALT and/or $AST \geq 3 \times ULN$ and concurrent $TBL \geq 1.5 \times ULN$
- ALT and/or $AST \geq 3 \times ULN$ and concurrent $TBL \geq 2 \times ULN$

7.4 Analysis of Vital Signs and Weight

The vital sign variables are defined in Section 4.3.4.³ Observed values of vital sign variables which are measured longitudinally will be summarized at each visit by the two treatment groups in Part 1 and by the four treatment groups in Part 2, respectively. Summary statistics such as number of subjects, baseline mean, visit mean, standard deviation, minimum and maximum will be provided.

The criteria for potentially clinically significant vital sign findings are presented in Table 2. The number and percentage of subjects meeting the criteria for potentially clinically significant vital sign values will be summarized by the two treatment groups in Part 1 and by the four treatment groups in Part 2. Vital sign results satisfying the criteria for potentially clinically significant findings will be identified in a listing.

Table 2. Criteria for Potentially Clinically Significant Vital Sign Findings

Vital Sign	Category	Criteria for Potential Clinically Significant Vital Signs
Systolic blood pressure	Low	Value \leq 90 mmHg and decrease \geq 20 mmHg from Baseline
	High	Value \geq 160 mmHg and increase \geq 20 mmHg from Baseline
Diastolic blood pressure	Low	Value \leq 50 mmHg and decrease \geq 15 mmHg from Baseline
	High	Value \geq 105 mmHg and increase \geq 15 mmHg from Baseline
Pulse	Low	Value \leq 50 bpm and decrease \geq 15 bpm from Baseline
	High	Value \geq 120 bpm and increase \geq 15 bpm from Baseline
Weight	High	> 7% increase from baseline
	Low	> 7% decrease from baseline

The last evaluation prior to the first dose of study drug in Part 1 or Part 2 will be used as Baseline for Part 1 or Part 2, respectively.

7.5 Analysis of ECG Parameters

No post-baseline ECGs were obtained for this study.

8.0 Summary of Changes**8.1 Summary of Changes Between the Previous Version and the Current Version**

Not applicable.

8.2 Summary of Changes in Previous Version

Not applicable.

9.0 Appendix

Appendix A. AESI List and Search Strategies

There are two types of search strategies may be used for categorizing AESI categories are as follow:

- Lowest Level MedDRA Queries (LMQs).
- Standard MedDRA Queries (SMQs)/Company MedDRA Queries (CMQs)/Product-specific MedDRA Queries (PMQs)

LMQs will be the default search strategy unless otherwise stated in the safety analysis request. SMQs/CMQs/PMQs will have limited use as a search strategy, e.g., aggregated safety review or any other special requests as deemed appropriate. LMQs will be used in our study.

The following table includes all AESI for Humira with the LMQ searches.

AESI	LMQ Name	LMQ Search Term Definition
Infection		
All Infection	Infection LMQ	Terms clearly identifying an infection.
Serious Infection	Infection LMQ	All Infections – Subset for SAEs.
Legionella Infection	Legionella Infection LMQ	Terms Legionella infections. Culture and isolation of Legionella from respiratory secretions and/or pleural fluid. Direct fluorescent antibody (DFA) staining that identifies Legionella in respiratory secretions and/or pleural fluid. Four-fold increase in Legionella antibody titer or a single titer of 1:128.
Diverticulitis	Diverticulitis LMQ	Leukocytosis, CT Findings (Phlegmon, free air bubbles, abscess, colonic wall thickening, free fluid, obstruction), Fistulas (colovesica, rectovaginal).

AESI	LMQ Name	LMQ Search Term Definition
Infection (continued)		
Opportunistic Infection Excluding Oral Candidiasis and TB	Opportunistic Infection LMQ	Terms describing unusually severe forms of infections by a microbe typically seen only in immunocompromised individuals e.g., the term 'Herpes sepsis' is included. Investigations for infections that generally occur exclusively in immunocompromised patients e.g., JC virus test positive. Broader terms for infections typically only seen in immunocompromised persons when a more specific term for that infection type is not available e.g., the term 'stomatoccal infection' is included. Terms describing specific forms of fungal infections or tuberculosis infections which typically occur only in immunocompromised patients e.g., the term 'disseminated TB' is included.
Oral Candidiasis	Oral Candidiasis LMQ	Terms describing Oral Candidiasis only.
Tuberculosis		Active tuberculosis and latent tuberculosis combined.
Active Tuberculosis	Active Tuberculosis LMQ	Terms that describe active disease of tuberculosis.
Latent Tuberculosis	Latent Tuberculosis LMQ	Terms that describe positive results for TB screening tests (either skin or blood tests). Terms that describe TB infection or latent infection.
Parasitic Infection	Parasitic Infection LMQ	Protozoal infectious disorders, Helminthic Disorders, and Ectoparasitic infestations. Skin and subcutaneous arthropod and parasitic infestations, Parasitic lower respiratory tract infections. Investigations terms for parasite identification and serology tests.
Reactivation of Hepatitis B	Reactivation of Hepatitis B Viral Infection LMQ	HBVsAg positive, HBeAb positive, PCR test for viral titer, HBVsAb positive, HBVc Ab positive.
Progressive Multifocal Leukoencephalopathy (PML)	Progressive Multifocal Leukoencephalopathy LMQ	PML definitive diagnosis.

AESI	LMQ Name	LMQ Search Term Definition
Malignancies		
Malignancies	Malignancies LMQ	
All MedDRA terms for malignant or unspecified tumors:
 
 • Malignancy related conditions. • Terms for malignancy related conditions. • Terms for therapeutic and diagnostic procedures used to treat malignancies; treated malignancy to be specified. • Some of these procedures are also used for the treatment of non-malignant conditions. • Laboratory tests (incl. the results) that are specific for the malignancies. • To make agreement on "in situ" stage whether they fall under malignancies or not; currently assessed as malignancies. • To make agreement on general terms of "neoplasm;" whether considered as malignancies when no further details provided. • Tumour markers. • Terms related to tumor markers including the result. 
For European Group on Tumour Markers, please reference the web site at http://ar.iiarjournals.org/content/27/4A/1901.abstract:
 
 • Terms related to benign tumors. • Terms related to premalignant conditions. • Treatment and diagnostic procedures that do not specify a malignancy indicated. • Malignancy related therapeutic and diagnostic procedures includes a variety of terms which describe chemotherapy or radiotherapy treatment. 
Please be aware, however, that there are some terms which relate to chemotherapeutic. Such terms are not linked to chemotherapy or radiotherapy terms.

Lymphoma	Lymphoma LMQ	
All terms for malignant or unspecified tumors.
 
Terms for malignancy related conditions.
 
Terms for therapeutic and diagnostic procedures used to treat malignancies.
 
Some of these procedures are also used for the treatment of non-malignant conditions terms related to tumor markers.

Hepatosplenic T-Cell Lymphoma (HSTCL)	Hepatosplenic T-Cell Lymphoma (HSTLC) LMQ	
The most specific inclusion criteria is the diagnosis based on T-cell histology for the lymphoma of T-cell receptor type.

Non-Melanoma Skin Cancer (NMSC)	Non-Melanoma Skin Cancer LMQ	
"Skin Neoplasms, Malignant and Unspecified" And Add the Preferred Terms.
 
"Squamous Cell Carcinoma" and "Bowen's Disease" to this Search.

AESI	LMQ Name	LMQ Search Term Definition
Malignancies (continued)		
Melanoma	Melanoma LMQ	The most common skin cancers are basal cell carcinoma and squamous cell carcinoma, but this category includes malignancies arising from other types of skin cells (e.g., Merkel cell carcinoma) and appendageal cells (e.g., eccrine carcinoma).
Leukaemia	Leukemia LMQ	Terms for Lymphoid leukemia (e.g., Acute lymphoblastic leukemia, ALL, Chronic lymphocytic leukemia, CLL). Terms for Myeloid leukemia (e.g., Acute myeloblastic leukemia, AML, Chronic myeloid leukemia, CML, Myeloid sarcoma). Terms for Monocytic leukemia (e.g., Acute monoblastic leukemia, Acute monocytic leukemia, AML, Chronic myelomonocytic leukemia). Terms for Other leukemia s of specified cell type (e.g., Acute erythroid leukemia). Terms for Leukemia of unspecified cell type. Terms for Leukemia in remission.
Other Malignancies Except Lymphoma, HSTCL, Leukemia, NMSC, and Melanoma		If an AE is identified as a "malignancy" in the "Malignancies LMQ" search above but not a "Lymphoma," "HSTCL," "Leukemia," "NMSC," or a "Melanoma," then it belongs to "Other Malignancies" category.
Immune Reactions		
Allergic Reactions Including Angioedema/ Anaphylaxis	Allergic Reactions LMQ	Any terms representing events which include anaphylaxis, allergic events, hypersensitivity, angioedema, angioneurotic edema, urticarial (hives).
Lupus-Like Reactions and Systemic Lupus Erythematosus (SLE)	Lupus-Like Reactions and Systemic Lupus Erythematosus (SLE) LMQ	Lupus erythematosus and associated conditions in both primary and secondary locations in this are included except Lupoid hepatic cirrhosis, which is excluded. Additional terms representing the diagnostic criteria of the American College of Rheumatology (ACR), e.g., Malar rash, Arthritis, Renal disorder, etc.

AESI	LMQ Name	LMQ Search Term Definition
Immune Reactions (continued)		
Vasculitis	Vasculitis LMQ	
Terms for primary vasculitides (e.g., Henoch-Schonlein purpura, Behçet's syndrome, or Granulomatosis with polyangiitis (which includes Wegener's granulomatosis).
 
Terms containing vasculitis (e.g., Cutaneous vasculitis, Lupus vasculitis, or Rheumatoid vasculitis).
 
Terms containing arteritis (e.g., Arteritis coronary or Polyarteritis nodosa).
 
Terms containing angiitis (e.g., Microscopic polyangiitis or Thromboangiitis obliterans).
 
Terms for forms of purpura indicative of a vascular condition such as Henoch Schonlein purpura and Chronic pigmented purpura (narrow, which includes Majocchi's purpura) and Palpable purpura (broad).
 
Terms for laboratory test results that may indicate vasculitis (e.g., Antineutrophil cytoplasmic antibody increased).

Cutaneous Vasculitis	Cutaneous Vasculitis LMQ	Terms for vasculitides clearly identifiable as cutaneous (e.g., Cutaneous vasculitis, Skin vasculitis, Majocchi's purpura, Leukocytoclastic vasculitis, vasculitis legs, Necrotizing vasculitis, polyangiitis or Vasculitic rash).
Non-Cutaneous Vasculitis		Terms for vasculitides that are NOT in Cutaneous Vasculitis LMQ.
Sarcoidosis	Sarcoidosis LMQ	Sarcoidosis of any organ.
Autoimmune Hepatitis	Autoimmune Hepatitis LMQ	
Cardiovascular/Vascular		
Myocardial Infarction	Myocardial Infarction LMQ	
Myocardial Infarction.
 
Terms which included the words 'myocardial infarction, heart attack, cardiac enzymes increased, cardiac troponin increased, CK-MB increased, ECG ST elevation, Q wave abnormal.'

Cerebrovascular Accident	Cerebrovascular Accident LMQ	Terms for conditions specific for cerebrovascular accident disorders irrespective of cause and irrespective of acuteness or chronicity.
Congestive Heart Failure	Congestive Heart Failure LMQ	
Terms describing existing cardiac failure in its various forms with or without right/left ventricular specified.
 
A small number of terms for symptoms, signs and investigational findings that are pathognomonic of the condition.

Pulmonary Embolism	Pulmonary Embolism LMQ	Terms that are specifically assigned to describe the condition where an embolic event occurred in the lung of a patient, chronic or acute, arterial or venous.

AESI	LMQ Name	LMQ Search Term Definition
Respiratory		
Interstitial Lung Disease	Interstitial Lung Disease LMQ	ILDs include inflammatory and fibrotic diseases that ultimately disrupt the alveolar capillary interface, leading to hypoxemia. ILDs usually manifest with a restrictive physiology, but airway involvement can cause obstruction or mixed physiology. ILDs are associated with many clinical settings, including connective tissue disease; occupational, environmental and drug exposures; and primary pulmonary disorders.
Gastrointestinal Events		
Intestinal Perforation	Intestinal Perforation LMQ	Terms for/related to any part of GI Tract, GI ulcers, obstruction, hemorrhage.
Intestinal Stricture in CD ^a	Intestinal Stricture LMQ	Abdominal Pain. Radiographic Findings: Bowl loop distension, gas-fluid level, bowel wall thickening.
Pancreatitis	Pancreatitis LMQ	Terms with the word "pancreatitis" (other than those indicative of chronic conditions). Terms indicative of pancreatic dysfunction (such as pancreatorenal syndrome). Terms for typical complications, e.g., Pancreatic pseudocyst.
Skin and Subcutaneous Tissue Disorders		
Stevens-Johnson Syndrome	Severe Skin Reaction Stevens-Johnson Syndrome LMQ	This falls within the erythema multiforme-toxic epidermal necrolysis spectrum, representing an intermediate severity. All terms and their synonyms specifically linked to erythema multiforme, Stevens Johnson syndrome, and toxic epidermal necrolysis are included. No procedure terms or appropriate investigation terms are specific.
Erythema Multiforme	Erythema Multiforme LMQ	Diagnosis terms that represent the condition Erythema Multiforme are included. Terms that represent the signs/symptoms that are specific for Erythema Multiforme and included in the criteria for the diagnosis of Erythema Multiforme are included.
Worsening and New Onset of Psoriasis	Worsening New Onset of Psoriasis LMQ	Psoriasis can present in guttate form, where the lesions are smaller, or involve flexural parts of the body (e.g., axilla, inframammary areas), or involve fingernails or toenails (i.e., nail psoriasis), or involve palms or soles. In pustular psoriasis, the presentation is characterized by sterile pustules on a brightly erythematous base. When pustular psoriasis involves the palms and soles, it is termed palmoplantar pustulosis. Other variants of psoriasis include psoriasiform dermatitis and acrodermatitis continua.

AESI	LMQ Name	LMQ Search Term Definition
Nervous System Disorder		
Demyelinating Disorders Including Multiple Sclerosis, Guillain-Barré Syndrome, and Optic Neuritis and Others	Demyelinating Disorders LMQ	Terms for encephalomyelitis and leukoencephalopathies related to demyelination (e.g., Acute haemorrhagic leukoencephalitis and Progressive multifocal leukoencephalopathy). Trigeminal neuralgia is included in broad terms due to possible association with multiple sclerosis or other demyelinating conditions. Terms representing a disability scale which is highly specific for MS (e.g., Expanded disability status scale score increased).
Amyotrophic Lateral Sclerosis	Amyotrophic Lateral Sclerosis LMQ	There are no specific tests to provide a definite diagnosis of ALS although the presence of upper and lower motor neuron signs in a single limb is strongly suggestive. The diagnosis is based on symptoms and signs as well as a series of tests to assess muscle weakness and atrophy, hyperreflexia, and spasticity which gets progressively worse. For these reasons the search terms recommended for adjudication purposes would need to be consistent with the diagnosis of ALS and not with non-specific findings describing all the different types of motor neuron diseases. Patients may exhibit symptoms and signs of the disease such as hyperreflexia, and spasticity. Tests such as muscle biopsy, nerve conduction velocity, electromyography as well as MRI scans of the brain or spinal cord may also point to a possible diagnosis of ALS although none of these tests are definitive and will therefore not be included in the search.
Amyotrophic Lateral Sclerosis (continued)		ALS-related syndromes include progressive muscular atrophy, primary lateral sclerosis and progressive bulbar palsy will be included in the search.
Reversible Posterior Leukoencephalopathy Syndrome (RPLS)	Reversible Posterior Leukoencephalopathy Syndrome (RPLS) LMQ	Reversible Posterior Leukoencephalopathy Syndrome definitive diagnosis. Posterior Reversible Encephalopathy Syndrome definitive diagnosis.
Hematologic Events		
Hematologic Disorders Including Pancytopenia	Hematologic Disorders Including Pancytopenia LMQ	Terms referring to direct alterations of the hematopoiesis. Hematological signs and diagnoses of bone marrow depression. Hematological investigation results of bone marrow depression. Neonatal terms are included in the broad search (the term neonatal does not allow a conclusion whether the condition is of acquired or inherited origin). Certain abnormal terms are included in the broad searches.

AESI	LMQ Name	LMQ Search Term Definition
Hepatic Events		
Liver Failure and Other Liver Events (Except Gall Bladder Related Events)	Liver Events LMQ	Terms representing liver related diagnoses or diagnoses that can be related histological descriptions. Also included are conditions associated with jaundice or cholestasis of possible hepatic origin and therefore excludes terms indicating jaundice caused by haemolytic conditions, such as Jaundice extrahepatic obstructive. Diagnoses associated with pregnancy are included.
Other		
Humira Administration Related Medication Error	Medication Errors LMQ	Medication errors. Product Quality Issues. Terms which included the words Medication errors that relates to 'adalimumab use.'
Injection Site Reactions	Injection Site Reaction LMQ	Terms in the Injection Site Reactions, Infusion Site Reactions, Vaccination Site Reactions. Terms which included the words injection site, infusion site, application site, administration site, and 'vaccination site.' The search is focused on local reactions to injections.

a. In CD program only. Any calculation of AE incident rate will only include patients in the CD program.

